### 5.6.3 Duration of Response (DOR) and Duration of Clinical Benefit

Duration of response (DOR) is defined as the time interval between the date of the earliest qualifying confirmed/unconfirmed response using irRC and the date of disease progression (PD) or death for any cause, whichever occurs first. DOR in months is calculated as: (date of PD or death – date of first confirmed/unconfirmed irCR/CR or irPR/PR + 1)/30.4375. DOR analysis will include only patients with confirmed/unconfirmed response of irCR/irPR using irRC.

For patients who are alive without documentation of disease progression following the qualifying response, duration of response will be censored following the same rule defined for PFS.

Duration of clinical benefit is defined as the time interval between the date of the earliest qualifying confirmed/unconfirmed best response using irRC and the date of progression disease (PD) or death for any cause, whichever occurs first. Duration of clinical benefit in months is calculated as: (date of PD or death – date of first confirmed/unconfirmed irCR/irPR or irSD + 1)/30.4375. Duration of clinical benefit will include only patients with confirmed/unconfirmed response of irCR/irPR or irSD using irRC.

For patients who are alive without documentation of disease progression following the qualifying response, duration of clinical benefit will be censored following the same rule defined for PFS.

Median DOR and duration of clinical benefit with the corresponding two-sided 95% CI will be estimated using the Kaplan-Meier method in each treatment group. The Kaplan-Meier curves will be presented.

DOR and duration of clinical benefit data will be presented in listing.

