- ^h Imaging studies during Follow-up will occur on Day 112 to 119 for patients receiving 6 doses of G100 or on Day 133 to 140 for patients receiving 9 doses of G100. Imaging studies should then occur every 8 weeks thereafter for the first year, every 3 to 4 months for the second year, and then at least every 6 months for the third and subsequent years.
- ⁱ Day 56 restaging CT or MRI scans should be performed if the optional treatment #9 is not given. If a PET CT is used, a standard high resolution CT series should be obtained rather than low resolution scans and only the CT imaging should be used to determine tumor measurements. PET scans should not be used to determine disease progression since it is expected that PET avidity will increase with the type of inflammation induced by this treatment and may lead to false positive results. Confirmation of disease progression by CT or MRI must be performed 4 or more weeks later per IrRC. If the 9th dose is given, then CT/MRI should be delayed to Day 63 to 77. Photographs: if the tumor can be measured and assessed visually, photographic documentation with measurements should be considered to keep a record and help assess any response to treatment (may be performed at any time during study)
- ^j A plasma sample for Pharmacokinetics/Pharmacodynamics analysis will be drawn within 2 hours prior to the first administration of G100 and 6 hours after the first administration of G100 or pembrolizumab, if applicable.

Immune Design

G100 (GLA-SE) and Pembrolizumab or Rituximab
Protocol IMDZ-G142; Version 04B; November 15, 2018

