10.3.22.2 Visits After Disease Progression (Every 8 to 12 Weeks)

Patients will receive telephone follow-up or clinic visit every 8 to 12 weeks after **confirmed** disease progression (or symptomatic deterioration with therapy) for at least 1 year after first study injection. Follow-up will include vital status (survival status), cancer status, and post-treatment anti-cancer therapy including time to next treatment, treatment details, and clinical response. If the patient agrees, the site may periodically (e.g., every 2 to 4 months) contact the patient beyond 1 year to check on vital and cancer status. Delayed objective responses have been observed on this study at >18 months from Day 0. Therefore, if the patient should experience a clinical regression and has not received any additional therapy, the patient may be asked for consent to collect clinical information such as imaging studies and biomarkers.

Any SAE that comes to the attention of the site staff that may be causally related to G100 must be reported to Immune Design, regardless of time elapsed. All AEs experienced from the time of enrollment through 30 days following cessation of pembrolizumab (and/or G100, whichever is longer) treatment will be reported by the investigator. Any ECI experienced through 30 days following cessation of treatment should be reported within 24 hours to the Sponsor. Any SAE due to any cause other than progression of the cancer under study that occurs through 90 days following cessation of pembrolizumab treatment, or 30 days following cessation of treatment if the subject initiates new anticancer therapy, whichever is earlier, must be reported within 24 hours to the Sponsor. After the 90-day reporting period, any SAE that comes to the attention

of the site staff that may be causally related to pembrolizumab must be reported to Sponsor regardless of time elapsed.

Note: Sections 10.3.23 to [10.3.29.2](#) apply only to patients enrolled on Part 5, G100 Plus Rituximab

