### 5.6.4 Progression-free Survival (PFS)

PFS is defined as time from date of first study treatment to date of first disease progression by irRC criteria, symptomatic deterioration, or death due to any cause, whichever occurs first. Progression-free survival (PFS) in months is calculated as: (date of first progression, symptomatic deterioration, or death (any reason) – date of first dose +1)/30.4375. The irRC modification requires a PD confirmation no less than 4 weeks from first documentation of progressive Disease (PD); once confirmed, the date of progression is defined as date of the first PD. In case of unconfirmed PD followed by symptomatic deterioration, the date of unconfirmed PD will be the date of progression. Patients without progression, symptomatic deterioration, or death are censored at the date of the last tumor assessment. If a patient begins a new anti-cancer therapy or has radiotherapy or surgery at a lesion site prior to confirmed progression (or death), the patient will be censored at the last assessment where the patient is documented as progression free prior to the intervention. Patients with two or more missing response assessments prior to a visit with progression (or death) will be censored at the last visit where the patient is documented to be progression free. Patients without disease assessment post-baseline will be censored at the first dose date. Table 7 below provides further details on how date of PFS event and date of PFS censoring are assigned.

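### SAP 5.6.3 gives two different start dates for duration of clinical benefit; under the one in the text, a later response shortens the duration

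*SAP*

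**What the plan says.** SAP 5.6.3 introduces the measure in words: "Duration of clinical benefit is defined as the time interval between the date of the earliest qualifying confirmed/unconfirmed best response using irRC", ending at PD or death. It then gives the calculation in months as "date of PD or death – date of first confirmed/unconfirmed irCR/irPR or irSD + 1)/30.4375". Responders and stable patients are pooled: "Duration of clinical benefit will include only patients with confirmed/unconfirmed response of irCR/irPR or irSD using irRC". Patients alive without progression are censored by the PFS rule. Kaplan-Meier medians with 95% confidence intervals, and curves, are planned in each treatment group.

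In the same section, duration of response starts at the "date of the earliest qualifying confirmed/unconfirmed response using irRC". That wording has no *best* in it, and it agrees with its own formula, which starts at the first complete or partial response.

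SAP 5.6.2 makes irSD the category for a patient who meets neither response criterion and has no irPD, so irSD at one scan can be followed by irPR or irCR at a later one. The protocol does not define duration of clinical benefit.

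**The concern.** Best response is the highest category a patient reaches; first irSD or better is the first scan on which the patient qualifies at all. For a patient who stays stable these are the same date. For a patient who is stable first and responds later they are not, and two programmers working from SAP 5.6.3 could produce different durations from the same data.

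The two rules also behave differently. If the clock starts at best response, the stable period before the response is dropped for responders but counted for patients who never respond. Because both groups enter one Kaplan-Meier estimate, a treatment group with more stable-then-respond patients would have its durations pulled down by that improvement.

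**Working it through.** The documents state no numerical result for this measure, so there is no figure to reproduce. The check applies the SAP's own formula to illustrative patients under each start date.

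**Inputs**
- Duration in months = (end day − start day + 1)/30.4375, from SAP 5.6.3.
- First restaging at Day 56 when dose 9 is not given (schedules of events), then imaging about every 8 weeks in year 1 (SAP 3.1).
- Assumed for illustration: scans exactly on Days 56, 112, 168, 224, 280 and 336; irSD at Day 56; PD at Day 336.

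**Stable-only patient.** Best response (irSD) and first irSD are both Day 56, so both rules give (336 − 56 + 1)/30.4375 = 281/30.4375 = 9.23 months.

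**irSD at Day 56, then irPR, same PD date**

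| First irPR | Text: start at best response | Formula: start at first irSD or better | Difference |
|---|---|---|---|
| Day 112 | 225/30.4375 = 7.39 | 9.23 | 1.84 |
| Day 168 | 169/30.4375 = 5.55 | 9.23 | 3.68 |
| Day 224 | 113/30.4375 = 3.71 | 9.23 | 5.52 |
| Day 280 | 57/30.4375 = 1.87 | 9.23 | 7.36 |

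The difference is the number of days from first irSD to first irPR, divided by 30.4375. Under the text, every responder in the table falls below the stable-only patient's 9.23 months. Under the literal formula all of them tie with that patient.

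**One exception under the formula.** A patient whose Day 56 scan is unconfirmed irPD and who has irPR at Day 112 starts at Day 112 and gets 7.39 months, against 9.23. Here the first qualifying scan really is later.

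**Starting at first treatment (Day 0).** With PD at Day 336, every patient above gets 337/30.4375 = 11.07 months.

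**The case against.** **The two wordings could be meant to agree.** One could read the text's earliest qualifying best response as simply the earliest scan at irSD or better. Then *best* does no work, and its absence from the parallel duration-of-response sentence is hard to explain. One could instead read the formula as first irCR or irPR for responders and first irSD for everyone else. That also removes the conflict, but the reversal then applies in full. Either reading has to be supplied by the reader.

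**The measure is minor.** This stands. It is a descriptive SAP summary with no test, threshold or decision attached. Responders have their own duration of response, and the data are listed, so a reader could recompute.

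**Stronger readings that the documents do not support**
- *That responders look worse because the clock does not start at treatment.* PFS does start there ("PFS is defined as time from date of first study treatment to date of first disease progression by irRC criteria"), but the reversal comes from the best-response start. Under the formula, which does not start at treatment either, the irSD-then-irPR patient ties with the stable-only patient.
- *That the protocol documents a stable-then-respond pattern.* It says "Delayed objective responses have been observed on this study at >18 months from Day 0", but in Protocol 10.3.22.2, which covers visits after progression. The synopsis likewise discusses late responses after initial irRC progression. Neither says that those patients had been stable until they responded.
- *That the formula cuts 56 to 77 days from every duration.* The upper figure comes from "If the 9th dose is given, then CT/MRI should be delayed to Day 63 to 77" (for example Protocol 3.5, footnote i). Part 5 allows at most 6 doses in the course and has no such delay. The Day 56 scan has a window of ±7 days, so Day 49 is possible. A patient who first qualifies at a later scan falls outside the range altogether. Calling the duration short also presupposes that first treatment is the right origin, which is a choice.

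**Conclusion.** The inconsistency is real and should be corrected: SAP 5.6.3 states two start dates that differ for any patient with irSD followed by irPR or irCR. In the illustration the same patient's duration changes by 1.84 to 7.36 months with the rule used. Under the text rule a responder gets a shorter duration than a stable-only patient with the same PD date; under the literal formula the two are equal.

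The sizes rest on an assumed scan grid and an assumed PD date. The existence of the conflict does not, and it needs no very late response: irSD at Day 56 and irPR at Day 112 is enough. How many patients follow that course cannot be told from the documents, so the effect on any treatment group's median is unknown. ORR, duration of response, sample size and error rates are untouched.

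**What to change.** In SAP 5.6.3, use one start date and make text and formula match. The smallest change is to delete *best* from the definition and state that the clock starts at the first assessment of irSD or better, as the formula has it. A later response then no longer shortens the duration. Duration of response stays as defined.

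Starting at first study treatment, in patients whose best response is irSD or better, is an acceptable alternative. irSD is judged without reference to any onset at the first scan, and PFS, OS and time to response all start at first treatment. If this is chosen, the SAP should say that the result is close to PFS restricted to a subgroup selected on a post-baseline outcome, and that it includes guaranteed event-free time up to the qualifying scan. It should also say whether symptomatic deterioration counts as an event: it does for PFS in SAP 5.6.4 but is not listed for this measure.

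The cost is one SAP sentence and one derivation line. If the SAP is not reopened, SAP section 1 already provides for documenting a reasoned deviation in the clinical study report.

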### 5.6.4 Progression-free Survival (PFS)

PFS is defined as time from date of first study treatment to date of first disease progression by irRC criteria, symptomatic deterioration, or death due to any cause, whichever occurs first. Progression-free survival (PFS) in months is calculated as: (date of first progression, symptomatic deterioration, or death (any reason) – date of first dose +1)/30.4375. The irRC modification requires a PD confirmation no less than 4 weeks from first documentation of progressive Disease (PD); once confirmed, the date of progression is defined as date of the first PD. In case of unconfirmed PD followed by symptomatic deterioration, the date of unconfirmed PD will be the date of progression. Patients without progression, symptomatic deterioration, or death are censored at the date of the last tumor assessment. If a patient begins a new anti-cancer therapy or has radiotherapy or surgery at a lesion site prior to confirmed progression (or death), the patient will be censored at the last assessment where the patient is documented as progression free prior to the intervention. Patients with two or more missing response assessments prior to a visit with progression (or death) will be censored at the last visit where the patient is documented to be progression free. Patients without disease assessment post-baseline will be censored at the first dose date. Table 7 below provides further details on how date of PFS event and date of PFS censoring are assigned.

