### **4.3 Efficacy Evaluable Population**

The Efficacy Evaluable population includes all enrolled patients without major protocol deviations, who have received at least one injection of G100, and have had baseline and at least one post-baseline disease assessment.

The Efficacy Evaluable population will be used for the tumor response analysis based on irRC, including overall tumor response and time to disease progression (TTP).

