## **5.6 Efficacy Evaluation**

Unless otherwise specified, efficacy analyses will be performed by part, treatment, and overall. A separate summary by treatment will be provided. Efficacy evaluation will be provided for the Efficacy Evaluable population. Efficacy evaluation based on the Safety population will be provided as a supportive analysis.

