**Table 7 Progression-Free Survival**

Situation	Date of Progression or Censoring	Outcome
No baseline tumor assessments	Date of first dose	Censored

Situation	Date of Progression or Censoring	Outcome
Progression documented between scheduled visits	Date of last radiological assessment of measured lesions (if progression is based on increase in sum of measured lesions)	Progressed
Symptomatic deterioration before first PD assessment	Date of Symptomatic deterioration	Progressed
Symptomatic deterioration between adequate assessment visits	Date of Symptomatic deterioration	Progressed
Symptomatic deterioration after two or more missed visit	Date of last tumor assessment	Censored
Death before first scheduled assessment	Date of death	Progressed
Death between adequately scheduled assessment visits	Date of death	Progressed
Death or progression after two or more missed visit	Date of last tumor assessment	Censored
New anti-cancer therapy or radiotherapy or surgery at a lesion site prior to confirmed progression (or death)	Date of last tumor assessment where the patient was documented as progression free prior to the intervention	Censored
No progression or death	Date of last tumor assessment	Censored

Summary of PFS including median, 95% CI, 25th and 75th percentiles, range, PFS rate at 3-month, 6-month, 9-month and 12-month will be estimated using the Kaplan-Meier method. The corresponding 95% CI for median will be calculated using the Brookmeyer and Crowley method. The Kaplan-Meier curve and swimmer plot will be displayed.

PFS analysis for the following subgroups will be presented:

- Relapsed/Refractory Patients
- Treatment Naïve Patients
- MR Patients
- MR and Abscopal Decrease Patients

PFS data will be presented in a data listing.

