### 5.6.5 Overall Survival (OS)

Overall Survival (OS) is defined as the time from date of first study treatment to death due to any cause. Overall survival in months is calculated as:  $(\text{date of death} - \text{date of first dose}) + 1) / 30.4375$ . Patients who are alive at the end of study will be censored at the last date the patient is known to be alive or data analysis cutoff date, whichever is earlier.

Summary of OS including median, 95% CI, 25th and 75th percentiles, and range will be estimated using the Kaplan-Meier method. The corresponding 95% CI for median will be calculated using the Brookmeyer and Crowley method. The Kaplan-Meier survival curve will be displayed.

OS data will be presented in a data listing.

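### PFS rules conflict for a treated patient who fails before any post-baseline disease assessment, and the main PFS and OS analyses leave that patient out

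*SAP*

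**What the plan says.** **PFS rules.** SAP 5.6.4 times PFS from first study treatment and counts progression by irRC, symptomatic deterioration or death from any cause as the event. Later in the same paragraph it says "Patients without disease assessment post-baseline will be censored at the first dose date". Table 7, which that paragraph introduces as giving further detail, has rows for "Death before first scheduled assessment" and "Symptomatic deterioration before first PD assessment". Both are scored as progressed, on the date of death or of deterioration. Table 7 has no row for a missing post-baseline assessment. Its only row that censors at first dose is for a missing baseline assessment.

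**Analysis sets.** SAP 4.3 limits the Efficacy Evaluable population to patients without major deviations "who have received at least one injection of G100, and have had baseline and at least one post-baseline disease assessment". SAP 5.6 then states "Efficacy evaluation will be provided for the Efficacy Evaluable population", and adds "Efficacy evaluation based on the Safety population will be provided as a supportive analysis". Neither 5.6.4 nor 5.6.5 names another population.

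**OS.** "Overall Survival (OS) is defined as the time from date of first study treatment to death due to any cause". Section 5.6.5 has no rule that censors at first dose.

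**Timing.** The first restaging is at Day 56 +/- 7, or at Day 63 to 77 if the ninth G100 dose is given (Protocol 10.3.8 and 10.3.20).

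**The concern.** Death or clinical deterioration before any assessment is the worst outcome a treated patient can have. The 5.6.4 sentence and Table 7 treat it in opposite ways, and the SAP does not say which prevails, so the choice is left to whoever programs the analysis of an open-label trial.

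The choice of main set adds to the problem. Both clocks start at first treatment, but entry to the set depends on something that happens later. A patient who fails before that point leaves the risk set instead of counting as an event. This is guarantee-time bias, and it can only raise the curve. The 3-month PFS rate that 5.6.4 asks for falls soon after the first restaging and is directly exposed.

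**Working it through.** The plan gives no sample size, power or event figure for PFS or OS, so there is no figure to reproduce. The numerical rules in SAP 3.4 concern ORR and CR and do not bear on this point.

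**Step 1. One patient under each rule.** Take a treated patient who dies on Day 30 with no post-baseline disease assessment.

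| Source | PFS | OS |
|---|---|---|
| SAP 4.3 with 5.6, main set | excluded | excluded |
| SAP 5.6.4, first-dose sentence | censored at first dose | no such rule |
| SAP 5.6.4 definition and Table 7 | event on Day 30 | not applicable |
| SAP 5.6.5, supportive Safety run | not applicable | event on Day 30 |

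Symptomatic deterioration follows the PFS column only if the patient is never assessed afterwards. A patient who deteriorates and is scanned later can meet 4.3, and Table 7 then scores the event.

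**Step 2. How many distinct results.** A patient censored at first dose is in no later risk set, so the Kaplan-Meier product is the same as if the patient had been excluded. PFS therefore has two distinct results: early failure removed, or early failure counted.

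**Step 3. General size.** Let e be the fraction of all treated patients who fail before any assessment, and S the true rate at a time after those failures. Then S = (1 - e) x (rate among the rest), so the reported rate is S / (1 - e). With assumed values, S = 40% gives 0.40/0.95 = 42.1% (e = 5%), 0.40/0.90 = 44.4% (10%) and 0.40/0.85 = 47.1% (15%).

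**Step 4. Illustration at the planned group sizes.** The sizes are from SAP 3.4: 12 per Part 2 arm and up to 25 treated in Part 3. Assumptions: k early failures on Day 30 with no assessment; 2 (n = 12) or 5 (n = 25) progressions on Day 80; everyone else followed past 3 months (91.3 days).

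| n | k | Removed (excluded or censored) | Counted as events | Difference (points) |
|---|---|---|---|---|
| 12 | 1 | 9/11 = 81.8% | 9/12 = 75.0% | 6.8 |
| 12 | 2 | 8/10 = 80.0% | 8/12 = 66.7% | 13.3 |
| 12 | 3 | 7/9 = 77.8% | 7/12 = 58.3% | 19.4 |
| 25 | 1 | 19/24 = 79.2% | 19/25 = 76.0% | 3.2 |
| 25 | 3 | 17/22 = 77.3% | 17/25 = 68.0% | 9.3 |

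The first row agrees with Step 3: e = 1/12, and 75.0% / (11/12) = 81.8%. With k = 0 all rules agree.

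For OS, if the early failures are deaths and nobody else dies by 3 months, the main set shows 100%. Counting them gives 11/12 = 91.7% for one death in 12 and 9/12 = 75.0% for three.

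**The case against.** The best defence is that the text can be read sensibly. Death is an event by definition, an earlier sentence in 5.6.4 confines last-assessment censoring to event-free patients, and the paragraph defers to Table 7 for detail. A careful programmer would probably follow Table 7. But the first-dose sentence lacks the condition that the earlier sentence carries, and nothing gives Table 7 precedence.

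A second defence is that SAP 4.3 itself names narrower uses: "The Efficacy Evaluable population will be used for the tumor response analysis based on irRC", with time to progression. That is true, and PFS and OS come in only through the general statement in 5.6. Still, 5.6.8 defines its own set for biomarkers, while 5.6.4 and 5.6.5 define none.

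Several stronger readings are tempting, and the documents do not support them:

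- *Early deaths vanish from OS altogether.* The first-dose rule belongs to PFS. The supportive Safety run counts these deaths in OS, and SAP 5.7.3 tabulates and lists all deaths. One gap remains: SAP 4.2 words the Safety Population as injected after local radiation, which Parts 4 and 5 do not receive (Protocol 8.3).
- *Nobody in the main set can die before the first scan.* SAP 4.3 asks for a disease assessment, which it does not define, and tumours are also measured by examination at dosing visits (for example Protocol 10.3.5). On that reading, some early deaths would stay in.
- *About two of the 22 Part 4 patients are lost at e = 10%.* The 22 are already efficacy evaluable and must have had a post-baseline assessment (SAP 3.4), so e is zero among them by construction.
- *The bias is present, and worst in Part 4.* No count of early failures is given. Eligibility requires ECOG 0 or 1 and a life expectancy of at least 6 months (Protocol 7.1), which argues for few of them.

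It also stands that PFS is a secondary endpoint and OS exploratory, and that the plan's numerical decision rules use ORR or CR.

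**Conclusion.** The point holds as a conflict of wording plus a main-set choice that can bias in only one direction. For a treated patient who dies, or who deteriorates and is never assessed, before any post-baseline disease assessment, the 5.6.4 sentence and Table 7 give opposite PFS outcomes. The main PFS and OS analyses omit the patient. The supportive run resolves this for OS, if its population is read to include Parts 4 and 5, but not for PFS, because the same conflict recurs there.

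The upward bias is conditional on such failures occurring. Its size is the factor 1/(1 - e), with e taken over all treated patients and not given in the documents. In the 12-patient illustration, one failure is worth 6.8 points of 3-month PFS; the Day 30 failure and the two later progressions are assumptions. No decision rule in the plan is affected, so this should be corrected but does not undermine the trial's primary conclusions.

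**What to change.** 1. Make all patients who received at least one dose of study treatment the main set for PFS and OS, with the Efficacy Evaluable run as supportive. Word the all-treated set so that it does not require prior radiation in Parts 4 and 5.
2. Reword the 5.6.4 sentence to: *Patients without post-baseline disease assessment who neither died nor had symptomatic deterioration will be censored at the first dose date.*
3. Add the matching row to Table 7: no post-baseline assessment, no death and no symptomatic deterioration; date of first dose; censored.

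The cost is SAP wording only. No new data are needed, and a run on a similar set is already planned as supportive. If the SAP can no longer be amended, its section 1 allows a justified deviation documented in the study report. The downside is that the reported rates may be slightly less favourable.
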